21.15 Appendix 15: Consensus Recommendations for the Uniform Reporting of Clinical Trials

Report of the International Myeloma Workshop Consensus Panel International Myeloma Workshop Consensus (IMWC) Response Criteria:

Stringent Complete Response (sCR):

Complete response (CR) as defined below plus:

- normal free light chain (FLC) ratio and
- absence of clonal cells in bone marrow (BM) by immunohistochemistry (IHC) or 2 to 4 color flow cytometry

Complete Response (CR):

- Negative serum and urine immunofixation, and
- Disappearance of any soft tissue plasmacytomas, and
- $\leq 5\%$ plasma cells in BM

Very Good Partial Response (VGPR):

- Serum and urine M-component detectable by immunofixation but not on electrophoresis

OR

- 90% or greater reduction in serum M-component plus urine M-component < 100 mg per 24 hrs

Partial Response (PR):

- $\geq 50\%$ reduction of serum M-protein and reduction in 24-hr urinary M-protein by $\geq 90\%$ or to < 200 mg per 24 hrs

AND

- If the serum and urine M-protein are not measurable, a $\geq 50\%$ decrease in the difference between involved and uninvolved FLC levels is required in place of the M-protein criteria. If serum and urine M-protein are not measurable, and serum FLC assay is also not measurable, $\geq 50\%$ reduction in BM plasma cells is required in place of M-protein, provided baseline BM plasma cell percentage was $\geq 30\%$, and in the size of the soft tissue plasmacytomas is also required.

Minimal Response (MR):

- $\geq 25\%$ but $\leq 49\%$ reduction of serum M-protein and reduction in 24-hr urinary M-protein by 50% to 89%

AND

- If present at baseline, 25% to 49% reduction in the size of soft tissue plasmacytomas is also required.
- No increase in size or number of lytic bone lesions (development of compression fracture does not exclude response).

Stable Disease (SD):

- Not meeting criteria for CR, VGPR, PR, MR or PD

Progressive Disease (PD):

Requires an increase of $\geq 25\%$ from lowest response value in any one or more of the following:

- serum M-component (absolute increase must be ≥ 0.5 g/dL), or
- urine M-component (absolute increase must be ≥ 200 mg/24 hr), or
- the difference between involved and uninvolved FLC levels (absolute increase must be >10 mg/dL): only for subjects without measurable serum and urine M-protein levels, or
- bone marrow plasma cell percentage (the absolute % must be $\geq 10\%$) – only for subjects without measurable serum and urine M-protein levels and without measurable disease by FLC level

- definite development of new bone lesions or soft tissue plasmacytomas or definite increase in the size of existing bone lesions or soft tissue plasmacytomas
 - development of hypercalcemia (corrected calcium >11.5 mg/dL or 2.65 mmol/L) that can be attributed solely to the plasma cell proliferative disorder
- a. All response categories (CR, sCR, VGPR, PR, MR and PD) require 2 consecutive assessments made at any time before the institution of any new therapy; CR, sCR, VGPR, PR, MR, and SD categories also require no known evidence of progressive or new bone lesions if radiographic studies were performed. VGPR and CR categories require serum and urine studies regardless of whether disease at baseline was measurable on serum, urine, both, or neither. Radiographic studies are not required to satisfy these response requirements. Bone marrow assessments need not be confirmed. For PD, serum M- component increases of more than or equal to 1 g/dL are sufficient to define relapse if starting M-component is ≥ 5 g/dL.
- b. Clarifications to IMWG criteria for coding CR and VGPR in subjects in whom the only measurable disease is by serum FLC levels: CR in such subjects indicates a normal FLC ratio of 0.26 to 1.65 in addition to CR criteria listed above. VGPR in such subjects requires a >90% decrease in the difference between involved and uninvolved FLC levels.
- c. Clarifications to IMWG criteria for coding PD: Bone marrow criteria for PD are to be used only in subjects without measurable disease by M protein and by FLC levels; “25% increase” refers to M protein, FLC, and BM results, and does not refer to bone lesions, soft tissue plasmacytomas, or hypercalcemia and the “lowest response value” does not need to be a confirmed value.

References:

Durie BGM, Harousseau J-L, Miguel JS, et. al. International uniform response criteria for multiple myeloma. *Leukemia*. 2006;20:1467-73.

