5.4.1.1.8 HCL

1. Histologically confirmed diagnosis of HCL according to morphological and immunophenotypic criteria of WHO classification [[WHO, 2008](#)] of lymphoid neoplasms.
2. Must have either:
 - **Refractory disease** defined as no response or disease progression in ≤ 1 year following first-line treatment with a purine analog (i.e., pentostatin, cladribine or fludarabine)
OR

- **Relapsed** disease defined as having relapsed following treatment with at least two prior treatments
3. Must have the presence of leukemic cells in the peripheral blood or BM aspirate or BM biopsy AND one or more of the following:
 - Bulky/symptomatic splenomegaly
 - Hemoglobin <10 g/dL
 - Platelets <100 × 10⁹/L
 - Absolute neutrophil count (ANC) <1 × 10⁹/L
 4. For subjects with an opportunistic infection: the infection must be adequately managed and the subject must be clinically stable. The investigator may discuss this issue with the Medical Lead.

5.4.1.1.9 MM

1. Histologically confirmed secretory MM.
2. Has received at least 2 prior lines of therapy, such as prior treatment with a proteasome inhibitor and IMiD, and is now refractory or has demonstrated intolerance (despite standard measures of supportive care and dose reduction) to the most recent therapy received
3. Must have measurable disease of MM as defined by at least **ONE** of the following:
 - Serum M-protein ≥1 g/dL (≥10 g/L)
 - Urine M-protein ≥200 mg/24 hr
 - Serum free light chain (FLC) assay: involved FLC level ≥5 mg/dL (≥50 mg/L) and an abnormal serum FLC ratio (<0.26 or >1.65), or
 - Biopsy proven plasmacytoma (measured within 28 days of Screening)
4. **For subjects with an opportunistic infection:** the infection must be adequately managed and the subject must be clinically stable. The investigator may discuss this issue with the Medical Lead.

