2.4.1 Primary endpoint

The primary efficacy assessment will be the evaluation of overall response rate (ORR) calculated as a proportion of the subjects who have a confirmed response relative to the total number of subjects in the analysis population. Clinical response to dabrafenib in combination with trametinib will be assessed according to the appropriately established response criteria for each histologic cohort. [Table 2-1](#) outlines the response criteria and subcategories for overall response for each histologic cohort. Following feedback on the WHO Grade 1 and 2 Glioma cohort from the FDA, additional summaries of best response and duration of response will be produced excluding Minor Response (MR) from the subcategories defined as Response for this cohort.

Table 2-1 Response Criteria and Definition of Response by Histology

Histology	Response Criteria	Response Subcategories defined as Overall Response
ATC, BTC, GIST, ASI	RECIST 1.1	CR, PR
NSGCT/NGGCT	RECIST 1.1; Serum tumor markers normalization or not will be considered as part of response criteria (serum tumor markers: AFP, β -HCG)	Marker-Negative CR (CR-), Marker-Positive CR (CR+), Marker-Negative Partial Remission (PR-), Marker-Positive Partial Remission (PR+)
WHO Grade 1 and 2 Glioma	Response Assessment Criteria for WHO Grade 1 or 2 Glioma: RANO Working Group	CR, PR, MR
WHO Grade 3 and 4 Glioma	Updated Response Assessment Criteria for WHO Grade 3 or 4 Glioma: RANO Working Group	CR, PR
MM	IMWG Uniform Response Criteria for MM	sCR, CR, PR, VGPR
HCL	Adapted from NCCN guidelines, Consensus Resolution Criteria and previous studies definition	CR without MRD (CR-MRD), CR with MRD (CR+MRD), PR

Abbreviations: AFP, alpha-fetoprotein; ASI, adenocarcinoma of the small intestine; ATC, anaplastic thyroid cancer; β -hCG, beta-human chorionic gonadotropin; BTC, biliary tract cancer; CR, complete response; GIST, gastrointestinal stromal tumor; HCL, hairy cell leukemia; IMWG, International Myeloma Working Group; MM, multiple myeloma; MR, minor response; MRD, minimal residual disease; NCCN, National Comprehensive Cancer Network; NGGCT, non-geminomatous germ cell tumor; NSGCT, non-seminomatous germ cell tumor; PR, partial response; RANO, Response Assessment for Neuro-Oncology; RECIST, Response Evaluation Criteria in Solid Tumors; sCR, stringent complete response; VGPR, very good partial response; WHO, World Health Organization

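### Read literally, the myeloma partial-response rule in Appendix 15 has no general plasmacytoma condition, so a subject with an unchanged plasmacytoma can count as a responder

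*Protocol*

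**What the plan says.** Protocol Section 7.5.2.3 (Table 8) sends the reader to Appendix 15 for the MM criteria. Appendix 15 gives three routes to PR:

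- **M-protein.** At least a 50% "reduction of serum M-protein and reduction in 24-hr urinary M-protein by" at least 90%, or to under 200 mg per 24 hours.
- **FLC, if M-protein is not measurable.** At least a 50% "decrease in the difference between involved and uninvolved FLC levels is required in place of the M-protein criteria".
- **Marrow, if FLC is not measurable either.** At least a 50% fall in marrow plasma cells "is required in place of M-protein, provided baseline BM plasma cell percentage was" at least 30%. This sentence then runs on with "and in the size of the soft tissue plasmacytomas is also required".

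Two other categories state a plasmacytoma condition on its own line. Complete response (CR) has "Disappearance of any soft tissue plasmacytomas, and". Minimal Response (MR) has "If present at baseline, 25% to 49% reduction in the size of soft tissue plasmacytomas is also required". VGPR, which ranks above PR, has none.

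Protocol Section 5.4.1.1.9 asks for at least one item of measurable disease, and one qualifying item is "Biopsy proven plasmacytoma (measured within 28 days of Screening".

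PR counts as response for MM in Protocol Table 31 and SAP Table 2-1. The SAP names the "IMWG Uniform Response Criteria for MM" without restating them, and its Table 2-3 covers confirmation only.

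**The concern.** A higher response category should not be more lenient about the same lesion than the one below it. As printed, MR looks at the plasmacytoma whenever one was present at baseline, while PR by M-protein or FLC does not look at it. PR is a success in the primary endpoint and MR is not, so the gap sits on the line between responder and non-responder.

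Little downstream would correct it. SAP Section 2.4.1 derives best response from the investigator's assessment at each time point, and SAP Section 2.6.2 notes that MM has no independent review. Two sites could classify the same subject differently, one following the printed PR text and the other reading a plasmacytoma condition into it. The result feeds the MM response rate and the hierarchical model with its 92% success rule (SAP Section 2.4.2).

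**Working it through.** No figure in the plan depends on this wording, so there is nothing to reproduce. The check applies the printed text to specific subjects.

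**Subject 1: M-protein responds, plasmacytoma unchanged.** Illustrative values: serum M-protein 3.0 to 1.4 g/dL, urine M-protein under 200 mg per 24 hours, a 4 cm plasmacytoma still 4 cm.

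- Serum fall = (3.0 − 1.4)/3.0 = 53%, which is at least 50%. The urine condition is met.
- The fallback sentence does not apply, because M-protein is measurable. Its plasmacytoma clause is never reached.
- Progression needs a new or definitely larger plasmacytoma, so an unchanged one is not progression.
- Result: PR, and a responder once a second consecutive assessment confirms it (SAP Table 2-3). The plasmacytoma change is 0%, which fails the plasmacytoma conditions of both CR and MR.

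**Subject 2: FLC only, FLC responds, plasmacytoma unchanged.** The FLC sentence ends without a plasmacytoma condition. Result: PR.

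With a general condition added to PR, subjects 1 and 2 are no longer PR.

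**Subject 3: plasmacytoma is the only measurable disease, baseline marrow plasma cells below 30%, plasmacytoma shrinks.** The fallback sentence can be read two ways:

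| Reading of the 30% proviso | PR route for subject 3 |
|---|---|
| It governs the whole fallback | None |
| It governs only the marrow requirement, and the plasmacytoma requirement stands | Yes, borrowing the 50% stated earlier in the sentence |

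The text does not settle which is meant. Under the first reading, adding a general plasmacytoma condition does not help this subject, because there is still no base criterion to satisfy. A separate rule is needed.

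**Subject 4: serum M-component falls 90%, urine under 100 mg per 24 hours, plasmacytoma unchanged.** Result: VGPR as printed. If only PR is corrected, PR becomes stricter about plasmacytoma than VGPR.

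**Size.** One reclassified subject changes the MM response rate by 100/n percentage points. The first three sizes below are the projected MM enrolments in Protocol Table 32; 25 is the cap on the primary analysis cohort.

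| n | 5 | 17 | 20 | 25 |
|---|---|---|---|---|
| Change (points) | 20 | 5.9 | 5 | 4 |

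**The case against.** **The intended meaning is inferred.** VGPR also lacks a plasmacytoma condition, so the category order alone does not prove that the authors meant PR to have one. This stands as a limit on what can be said about intent. It leaves the inconsistency with CR and MR in place, and it means that the repair must cover VGPR.

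**The clause may be a layout fault.** A line break lost in conversion from PDF could explain the grammar, and there is no second copy of Appendix 15 to compare. This cannot be excluded. The clause would still lack its own percentage and any statement of whom it covers.

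**The plasmacytoma-only subject may not be shut out.** A reader might infer that such a subject can never be PR and, short of CR, must be a non-responder. The documents do not support that. The proviso has a second reading that leaves a PR route open. Entry also requires secretory myeloma, so M-component may be detectable by immunofixation but not electrophoresis, which literally meets one branch of VGPR.

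**One subject need not change the decision.** A reader might infer a flip from a cohort-alone calculation. Using the Appendix 6 priors without borrowing (mean effect with variance 3, between-histology variance IG(3, 0.5), control 15%), the posterior probability is 0.84 at 3/10 and 0.91 at 3/8, both below 0.92. The protocol's own examples with borrowing, for another histology with the same 15% control, give 0.96 at 3/10 (Example 1) and 0.94 at 3/8 (Example 5), both declared successes. The objection is right: the decision depends on the other cohorts, and no specific flip should be claimed.

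**Reach is unknown.** This is one of nine cohorts, and only subjects with a baseline plasmacytoma are affected. That is correct, and it limits the weight of the point.

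**Conclusion.** The point holds as a defect in the definition of a primary-endpoint response. Read literally, PR by M-protein or FLC needs no plasmacytoma shrinkage, although CR and MR have stand-alone plasmacytoma conditions. It concerns unchanged or insufficiently shrunk lesions only, since definite growth is progression. For plasmacytoma-only disease with baseline marrow plasma cells below 30%, the finding is ambiguity about a PR route, not proof that none exists.

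The size is 1/n per reclassified subject. The final MM sample size and the number with baseline plasmacytoma are not in the documents, and no misclassified subject is shown. The conclusion rests on Appendix 15 being the rule that investigators applied. The wording should be corrected and the affected records re-checked; the documents give no ground for saying that the MM result is wrong.

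**What to change.** In Appendix 15, or in a clarification in the SAP:

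1. End the PR fallback sentence at the marrow proviso.
2. Add a separate PR bullet for every subject with a soft-tissue plasmacytoma at baseline, requiring its size to fall by at least 50%. This is the percentage already in that sentence.
3. State how PR is assigned when a plasmacytoma is the only measurable disease, including when baseline marrow plasma cells are below 30%.
4. State whether the same condition applies to VGPR, so that PR is not stricter than the category above it.
5. Before the final analysis, re-check the recorded responses of MM subjects with baseline extramedullary disease against the clarified text, and report any that change.

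The cost is a wording change and a review of the MM subjects with baseline extramedullary disease. The data should already exist: Protocol Table 4 schedules extramedullary assessment every 8 weeks, and its footnote 37 asks for clinical examination at each response visit. The MM response rate could move in either direction.

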21.16 Appendix 16: Imaging Guidelines for WHO Grade I or II Glioma

Basic MRI protocol:

- Axial FLAIR (canthomeatal alignment): 3 to 5 mm sections, 1 mm interslice gaps, slice registration preserved as much as possible between sequential studies
- Axial T2: 5 mm sections, 1 mm interslice gap
- Coronal T1: 5 mm sections, 1 mm interslice gap
- Post-gadolinium chelate (contrast agent per local clinical practice): coronal T1, axial T1

Alternatively pre-gadolinium and post-gadolinium volumetric T1 may replace axial and coronal T1-weighted sequences.

Supplementary imaging methods:

- Two-dimensional or 3-dimensional spectroscopic imaging (MR spectroscopy)
- Perfusion imaging (DSC-MRI)
- Diffusion-weighted imaging (-B=0, B=1000)

PET imaging:

For ^{11}C -MET and ^{18}F -FET PET:

- Subject must fast for 4 hrs prior to imaging
- Images must be obtained in a supine position
- 10 min transmission scan must be done prior to tracer application
- C-MET or F-FET administered intravenously as a bolus injection of 740 MBq (20 mCi; MET) or 370 MBq (10 mCi; FET)

- Accumulation of tracer will be recorded over 60 min in 47 transaxial slices of entire brain
- Spatial resolution of C-MET PET and F-FET PET: 6 mm or better in all dimensions
- SUV, T/B ratios and uptake kinetics: calculated in tumor and corresponding mirror regions

Abbreviations: DSC, dynamic susceptibility contrast; FET, ¹⁸F-fluoroethyltyrosine; FLAIR, fluid attenuation inversion recovery; MET, ¹¹C-methionine; PET, positron emission tomography; SUV, standard uptake value; T/B, tumor background ratio

References:

van den Bent MJ, Wefel JS, Schiff D, et al. Response assessment in neuro- oncology (a report of the RANO group): assessment of outcome in trials of diffuse low grade gliomas. *The Lancet*. 2011;12:583-593.

21.17 Appendix 17: Volumes of Collected Blood Samples

Assuming a subject remains on treatment for a period of 6 months, the total blood volume collected is estimated to be 306 mL (excluding any unpredictable events that would require additional blood samples to be obtained [REDACTED]).

Reason for Blood Sample	Screening	Day 1	Day 15	Week 4	Week 8	Week 12	Week 16	Trmt Disc
PK Analysis	N/A	N/A	N/A	4mL	2mL	2mL	N/A	2mL
[REDACTED]								
BRAF V600E (HCL and MM cohorts only)	3mL	N/A	N/A	N/A	N/A	N/A	N/A	N/A
PD and Biomarker Analyses	21mL	N/A	18mL	N/A	N/A	N/A	N/A	18mL
Clinical Laboratory Assessments	17mL	17mL	N/A	17mL	17mL	17mL	17mL	17mL
TOTAL Volume	38mL	23mL	18mL	21mL	19mL	19mL	17mL	37mL
[REDACTED]								

Abbreviations: HCL = Hairy Cell Leukemia; MM = Multiple Myeloma; PD = pharmacodynamics; [REDACTED]; [REDACTED]; PK = pharmacokinetics; Trmt Disc = treatment discontinuation

21.18 Appendix 18: Liver Safety Drug Restart or Rechallenge Guidelines

If subject meets liver chemistry stopping criteria do not restart/rechallenge subject with study treatment unless:

- Novartis Medical Governance approval **is granted** (as described below),
- Independent Ethics Committee (IEC) and/or institutional review board (IRB) approval is obtained, if required, and
- Separate consent for treatment restart/rechallenge is signed by the subject

If Novartis Medical Governance approval to restart/rechallenge subject with study treatment

is not granted, then subject must permanently discontinue study treatment and may continue in the study for protocol-specified follow-up assessments.

1. Rechallenge Following Liver Stopping Events that are Possibly Related to Study Treatment

Following drug-induced liver injury (DILI), **drug rechallenge is associated with a 13% mortality across all drugs in prospective studies** [Andrade, 2009] Clinical outcomes vary by drug, with nearly 50% fatality with halothane readministered within 1 month of initial injury. However, some drugs seldom result in recurrent liver injury or fatality.

Risk factors for a fatal drug rechallenge outcome include:

- hypersensitivity¹ with initial liver injury (e.g. fever, rash, eosinophilia)
- jaundice or bilirubin >2xULN with initial liver injury (direct bilirubin >35% of total)
- subject currently exhibits severe liver injury defined by: ALT \geq 3xULN, bilirubin \geq 2xULN (direct bilirubin >35% of total), or INR \geq 1.5
- serious adverse event or fatality has earlier been observed with drug rechallenges [Papay, 2009; Hunt, 2010]

- evidence of drug-related preclinical liability (e.g. reactive metabolites; mitochondrial impairment) [Hunt, 2010]

Rechallenge refers to resuming study treatment following DILI. Because of the risks associated with rechallenge after DILI this should only be considered for a subject for whom there is compelling evidence of benefit from a critical or life-saving medicine, there is no alternative approved medicine available, and a benefit:risk assessment of rechallenge is considered to be favorable.

Approval by the sponsor for rechallenge with study treatment can be considered where:

- Investigator requests consideration of rechallenge with study treatment for a subject who is receiving compelling benefit with study treatment that exceeds risk, and no effective alternative therapy is available.
- EC or IRB approval for rechallenge with study treatment must be obtained, as required.
- If the rechallenge is approved by Novartis Medical Governance in writing, the subject must be provided with a clear description of the possible benefits and risks of study treatment administration, including the possibility of recurrent, more severe liver injury or death.
- The subject must also provide signed informed consent specifically for the rechallenge with study treatment. Documentation of informed consent must be recorded in the study chart.
- Study treatment must be administered at the dose specified by the sponsor.
- Subjects approved by Novartis Medical Governance for rechallenge with study treatment must return to the clinic twice a week for liver chemistry tests until stable liver chemistries have been demonstrated and then standard laboratory monitoring may resume as per protocol.
- If after study treatment rechallenge, subject meets protocol-defined liver chemistry stopping criteria, study treatment should be permanently discontinued.
- Medical Lead, and the IEC or IRB as required, must be informed of the subject's outcome following study treatment rechallenge.
- The sponsor to be notified of any AEs, as per Section 11.

2. Restart Following Transient Resolving Liver Stopping Events NOT Related to Study Treatment

Restart refers to resuming study treatment following liver stopping events in which there is a clear underlying cause (other than DILI) of the liver event (e.g. biliary obstruction, pancreatic events, hypotension, acute viral hepatitis). Furthermore, there should be no evidence of alcoholic hepatitis or hypersensitivity, and the study treatment should not be associated with HLA markers of liver injury.

Approval by the sponsor for study treatment restart can be considered where:

- Investigator requests consideration for study treatment restart if liver chemistries have a clear underlying cause (e.g., biliary obstruction, hypotension and liver chemistries have improved to normal or are within 1.5x baseline and ALT <3xULN).
- Restart risk factors (e.g. fever, rash, eosinophilia, or hypersensitivity, alcoholic hepatitis, possible study treatment-induced liver injury or study treatment has an HLA genetic marker associated with liver injury (e.g. lapatinib, abacavir, amoxicillin/clavulanate) are reviewed and excluded.
- IEC or IRB approval of study treatment restart must be obtained, as required.
- If restart of study treatment is approved by Novartis Medical Governance in writing, the subject must be provided with a clear description of the possible benefits and risks of study treatment administration, including the possibility of recurrent, more severe liver injury or death.
- The subject must also provide signed informed consent specifically for the study treatment restart. Documentation of informed consent must be recorded in the study chart.
- Study treatment must be administered at the dose specified by the sponsor.
- Subjects approved by Novartis Medical Governance for restarting study treatment must return to the clinic once a week for liver chemistry tests until stable liver chemistries have been demonstrated and then laboratory monitoring may resume as per protocol.
- If after study treatment re-start, subject meets protocol-defined liver chemistry stopping criteria, follow usual stopping criteria instructions.
- Medical Lead, and the IEC or IRB as required, must be informed of the subject's outcome following study treatment restart.
- The sponsor to be notified of any AEs, as per Section 11.

References:

Hunt, CM. Mitochondrial and immunoallergic injury increase risk of positive drug rechallenge after drug-induced liver injury: A systematic review. *Hepatology.* 2010;52:2216-2222.

